10. STUDY TREATMENT

10.1. Investigational Study Medication

The study medication for this study is open label A-101 45%. All study medications are clear, colorless solutions which are indistinguishable in physical appearance.

Table 4: Study Medication Information

Study Medication Name	A-101 45%
Manufacturer	James Alexander Corporation, Blairstown NJ
A-101 concentration (%)	45
Pharmaceutical Form	Solution
Storage Conditions	59°F to 77°F (15°C to 25°C) protected from excessive heat, open flame and combustibles, out of direct sunlight and in a well-ventilated, dry area*
Route	Topical
Frequency	A-101 Study Medication will be applied twice a week for 8 weeks.
Duration of Administration	Apply study medication to each identified common wart for approximately 15 seconds. Allow each treated wart to remain undisturbed for approximately 15 seconds. Repeat the application/waiting cycle until the study medication has been applied to each identified common wart up to 3 times.
Activated Applicators	Activated applicators are stable for 4 hours at room temperature (59°F to 77°F or 15°C to 25°C)

*Excursions from these temperature ranges must be reported to Aclaris.

10.2. Subject Randomization

This is an open label study.

10.3. Study medication packaging, storage, and dispensing

A-101 Topical Solution 45% will be provided by Aclaris Therapeutics, Inc. and labeled according to applicable regulatory requirements.

The study medication will be packaged in single use applicators. The ampoule is provided inside a sealed polyethylene tube with a flocked, doe foot applicator on one end.

Aclaris Therapeutics, Inc.

Protocol Number: A-101-WART-303

Protocol Version 3: 14 February 2019

Open label subject kits will contain 20 A-101 Topical Solution 45% applicators. The subject kits will remain at the investigational site and the site staff will dispense study medication applicators to the subject for the at home treatment visit. The outside of each subject kit and each individual treatment applicator will be labelled in compliance with applicable regulatory requirements.

A-101 study medication must be stored in a location where there is limited access at 59°F to 77°F (15°C to 25°C) protected from excessive heat, open flame and combustibles, out of direct sunlight and in a well-ventilated, dry area. Proper storage of the A-101 study medication must be reviewed with the subject prior to dispensing the A-101 study medication applicators that are to be used at home.

Investigational study medication supplies are only to be used for subjects properly consented and randomized to this study.

10.4. Drug Accountability

The investigator or designee will maintain an accurate record of the receipt of the study medications as shipped by Aclaris Therapeutics, Inc. (or designee), including the date received and the condition of the study medications. One copy of this receipt will be returned to Aclaris Therapeutics, Inc. (or designee) when the contents of the study medication shipment have been verified and one copy maintained in the study file. In addition, an accurate study medication disposition record will be kept, specifying the amount dispensed for each subject and the date of dispensing. This inventory record will be available for inspection at any time. At the completion of the study, the original inventory record will be available for review by Aclaris Therapeutics, Inc. upon request.

Final drug accountability will be completed by the CRA at the completion of the study and all unused study medication will be destroyed after accountability has been completed.

10.5. Study Medication Treatment

The study medications are for external, topical use only and are to be applied only to those subjects that have been properly consented and randomized to the study.

The investigational center staff member must comply with the study medication storage conditions outlined in Section 10.1.

Subjects who have warts identified for treatment with A-101 Topical Solution, 45% will be instructed to treat each wart according to the technique outlined in Section 10.7. Subjects that are 18 years of age and older will apply their own study medication and subjects age 1 to 17 will have their study medication applied by a parent or legal guardian.

Identified warts are to be treated twice a week for up to 8 weeks (maximum 16 applications) or until the wart has cleared. Subjects are to be instructed to apply the A-101 study medication on the following days: Day 1, Day 4, Day 8, Day 11, Day 15, Day 18, Day 22, Day 25, Day 29, Day 32, Day 36, Day 39, Day 43, Day 46, Day 50 and Day 53. A window of +1 day is allowed.

Subjects (or parents/legal guardians) are to apply the A-101 study medication in the office on the following days: Day 1 and Day 29.

[figure not shown]
10.6. Preparing the Study Medication for Application

To perform a study medication treatment for the identified common wart a staff member will select the appropriate study medication applicator from the identified subject's kit. The following instructions outline the procedure for application of the study medication to the identified common wart. During each in-office treatment visit, the Investigational Study Staff will be responsible for reviewing the following instructions with the subject/parent/legal guardian and ensure that they understand how to properly prepare the applicator and apply the A-101 study medication.

- For the in-office treatment applications, the Investigational Study Staff member instruct the subject/parent or guardian to:
 - Washing their hands prior to applying the study medication.
 - Wear nitrile or vinyl examination gloves during the treatment; **latex gloves are prohibited.**
 - Visually inspect the applicator for damage:
 - If the applicator appears damaged do not use it for the treatment, contact the study monitor for disposal instructions and select an unused applicator with the next highest number for the treatment

If the applicator is intact, proceed with the applicator preparation process as outlined in [Figure 2](#).

Figure 2: Diagram Showing the Process for Preparing A-101 Study Medication

1. Each common wart should be cleaned using an alcohol wipe prior to application of A-101 45%.
2. Hold the applicator so that the applicator cap is pointing up.
3. Crush the ampule in the applicator by applying pressure to the center of the barrel of the applicator.
4. Remove the sleeve.
5. Tap the barrel of the applicator to ensure the solution is free of the crushed ampule.
6. Gently remove the cap by twisting while pulling away from the applicator.
7. Express a single drop of A-101 45% so that the tip of the applicator becomes wet.
8. Apply the solution to the identified warts in a circular motion.

All subjects will be supplied with treatment application instruction sheets at the completion of each in-office visit.

10.7. Applying Study Medication

All subjects that are between the ages of 1 and 17 will have their A-101 study medication applied by a parent/legal guardian. Parents/legal guardians of children must ensure that the child does not put the treated area in their mouth, or eyes, until completely dry after the application. If the treated area is not completely dry 10 minutes after the application, the area should be blotted dry.

Subjects 18 years of age and older will apply their A-101 study medication to his/her identified common warts. Study medication will be applied in the office on Day 1 and Day 29 prior to the PWA being performed.

The following instructions will be used by all subjects/parents/legal guardians applying A-101 study medication to all identified common warts:

- Do not apply the study medications to eyes, nose, mouth, mucous membranes, or open wounds
- Thoroughly cleanse the common wart by firmly rubbing with a swab/wipe wetted with 70% isopropyl alcohol
- Using firm pressure and with the tip of the applicator held over the wart, squeeze in the middle of the applicator to apply one drop of study medication onto the common wart. Using the smaller side of the applicator tip, move the applicator around in a circular motion to fully saturate the lesion. Apply the study medication for approximately 15 seconds.
- Minimize exposure to the surrounding normal skin
- During the treatment process remove excess study medication from the surrounding skin using a clean absorbent wipe.
- Ensure the identified common wart is fully saturated with study medication at the end of the ~15 second application
- Allow the treated wart to remain undisturbed for ~15 seconds
- After ~15 seconds repeat the ~15 second application process
- Repeat the application/waiting cycle until the study medication has been applied to each identified Wart up to 3 times.
- If severe erythema and edema develop, then the treatment cycle should be discontinued for that specific treatment application.
- Absorb any remaining A-101 study medication and dry the common wart and the surrounding skin without wiping or rubbing.

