9.2. Common Wart Dimensions and Physician's Wart Assessment (PWA)

Each identified wart that will be treated with A-101 study medication will be measured using the Aclaris supplied ruler. The longest axis of each identified wart will be documented on the subject's eCRF.

The Physician's Wart Assessment (PWA) is the Investigator's assessment of the severity of each identified common wart at a particular time-point. The Investigator should NOT refer to any other assessments to assist with this evaluation. This evaluation IS NOT a comparison with the PWA performed at any other visit.

During an 8-week treatment period, subjects will have their identified warts assessed using the PWA at the following time-points: Day 1, Day 29, Day 60 and Day 182.

The Investigator will assess each identified common wart and report the one integer that best describes the common wart severity using the following scale.

Physician's Wart Assessment	
Grade	Descriptor
0	Clear: No visible wart. No further treatment is indicated
1	Near Clear: a visible wart that is less than 3 mm in maximal diameter (or length)
2	A visible wart \geq 3 mm and $<$ 6 mm in maximal diameter (or length)
3	A visible wart \geq 6 mm in maximal diameter (or length)

The physician is encouraged to use a ruler or caliper and to feel the wart or skin area to help his/her assessment.

Common warts that are assessed by the investigator as having cleared (PWA =0) will be instructed not to continue to apply the A-101 study medication.

Refer to [Appendix 2](#) for the PWA Site Manual.

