### 3.4 Baseline and Analysis Visit

For the analysis of efficacy data, data will be assigned to an analysis visit within a treatment cycle based on period study day. These analysis visits are presented in [Appendix A](#).

For subjects who are not treated, baseline values are non-missing values prior to the start of the study. For treated subjects, baseline values are last non-missing values prior to first application of study medication. For analysis by treatment cycle, baseline values are last non-missing values before the start of a treatment cycle.

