### **3.11.1 Extent of Exposure**

The duration of treatment, the number of application days (i.e. the actual count of days where an application occurred), the mean applications per wart (for each subject the sum of all applications across all treated warts and all application days divided by the total number of treatments for all treated warts), and the total applications will be summarized using descriptive statistics (n, mean, SD, median, minimum and maximum). The percentage of total wart treatments that were performed in 1, 2 or 3 applications is also provided.

Overall compliance is calculated as the total number of wart treatments performed during the treatment period (through date of last application to any wart) divided by the total number of wart treatments expected to be performed. The total number of warts treated is the sum of the retreatment and home application diary records completed times the number of warts assessed at baseline minus the number of warts scored as PWA=0 or having an LSR grade 3 at the most recent assessment (<= the date of the application).

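### Protocol 10.7 puts the Day 1 and Day 29 in-office dose before the PWA, so a wart already clear at Day 29 could get one unneeded application; probably an inverted order, and minor

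*Protocol*

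**What the plan says.** Protocol 10.7 fixes the order of steps at the two in-office dosing visits: "Study medication will be applied in the office on Day 1 and Day 29 prior to the PWA being performed".

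The other texts that bear on this order are:

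- **When to stop (Protocol 10.5):** "Identified warts are to be treated twice a week for up to 8 weeks (maximum 16 applications) or until the wart has cleared".
- **PWA grade 0 (Protocol 9.2, repeated in Appendix 2):** "Clear: No visible wart. No further treatment is indicated". Section 9.2 adds that application ceases for warts the investigator has scored PWA=0.
- **PWA days (Protocol 9.2):** "subjects will have their identified warts assessed using the PWA at the following time-points: Day 1, Day 29, Day 60 and Day 182".
- **Local skin reactions (Protocol 12.1):** at treatment visits these are assessed before any application.
- **Baseline (SAP 3.4):** "For treated subjects, baseline values are last non-missing values prior to first application of study medication"; and "For analysis by treatment cycle, baseline values are last non-missing values before the start of a treatment cycle".
- **Wart-treatment count (SAP 3.11.1, compliance paragraph):** the count subtracts "warts scored as PWA=0 or having an LSR grade 3 at the most recent assessment (<= the date of the application".

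Table 2 of the protocol marks the PWA and the application at the same visits but states no sequence. No section gives a reason for dosing first.

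**The concern.** The PWA score is the formal trigger for stopping treatment of a wart. If the dose comes first, the decision not to dose at Day 29 is made after the Day 29 dose. A site that follows 10.7 to the letter could apply 45% peroxide to a place where no wart is visible.

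The order affects three smaller things:

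- The Day 29 PWA feeds clearance by visit and time to clearance, yet it would be read just after an application. The dosing schedule has no dose on Day 60 or Day 182 unless a new course starts then.
- A Day 1 PWA read after the first dose is not a baseline value as SAP 3.4 defines it.
- The SAP 3.11.1 count compares dates only. It implicitly assumes that a same-day PWA precedes the dose, which is the reverse of 10.7.

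**Working it through.** **Inputs.** The dose days come from Protocol 10.5: 1, 4, 8, 11, 15, 18, 22, 25, 29, 32, 36, 39, 43, 46, 50, 53. The PWA days come from Protocol 9.2: 1, 29, 60, 182. I read the day numbers as days within a course.

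**Step 1. Reproduce the plan's figure.** The list holds 16 days, which matches the stated maximum of 16 applications. Day 29 is the ninth.

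**Step 2. Which PWA can stop dosing within a course?** It must fall after the first dose (Day 1) and no later than the last (Day 53). Only Day 29 does.

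**Step 3. Doses given before each PWA.** With the dose first, count dose days on or before the PWA day. With the PWA first, count dose days strictly before it.

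| PWA day | Dose first (10.7) | PWA first |
|---|---|---|
| 1 | 1 | 0 |
| 29 | 9 | 8 |
| 60 | 16 | 16 |
| 182 | 16 | 16 |

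**Step 4. What the Day 29 PWA can still prevent.** With the PWA first: 16 − 8 = 8 doses (numbers 9 to 16). In the 10.7 order: 16 − 9 = 7 doses (numbers 10 to 16). The difference is one dose per wart already clear at Day 29, or 1/16 = 6.25% of a full course.

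**Step 5. Baseline.** In the 10.7 order one dose precedes the Day 1 PWA, so that reading falls outside both SAP 3.4 definitions. Some warts may have an earlier reading that qualifies, for example a Day 60 PWA when a repeat course starts then. A parent-study Visit 13 value could also serve if carried over, but SAP 3.11 mentions that visit only for laboratory values. A new wart would have no earlier reading. I then looked for a use of baseline PWA grade in SAP 3.10 and found none. The endpoints are complete clearance, duration of clearance, percent of warts clear, clearance in single-wart subjects and time to clearance. Having a single wart at baseline is a count, available from wart identification at Visit 1. The wart summaries in SAP 3.7 use identification, dimension and location.

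**Step 6. The SAP 3.11.1 count.** Take a wart dosed on Day 29 and then scored PWA=0 the same day. The assessment date is not later than the application date, so the wart is subtracted for that day. Treatments given: 9. Treatments counted: 8. One treatment that was given is left out. The expected number of treatments, which is the denominator of compliance, is not defined. If it uses the same subtraction, the effect may cancel partly or wholly. The separate count of application days in SAP 3.11.1 is based on actual application days and is unaffected.

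**The case against.** The strongest reply is that the protocol, read as a whole, does not require a clear wart to be dosed. Section 10.5 limits treatment to the time until clearance and does not tie that limit to a PWA score. Section 12.1 has the investigator examine each wart site for skin reactions before the dose, so clearance can be seen in time. A wart that clears between visits can also be dosed at home before any PWA, whatever the order at Day 29. No planned efficacy result is shown to change, and efficacy is descriptive only.

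Most of this stands, and it limits the point to what could happen. It does not rescue the sentence. The skin reaction check grades irritation and does not ask whether the wart is still there. The formal stop in 9.2 is the PWA score, and 10.7 puts that score after the dose.

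A reader might infer more than the documents support:

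- **That 9.2 is breached.** Read literally, it bars only doses after a PWA=0 score.
- **That the technique instruction "Minimize exposure to the surrounding normal skin" forbids the extra dose.** It concerns spill-over around a wart under treatment and says nothing about a cleared site.
- **That Table 2, footnote 6 settles the order.** It governs dispensing for a new course, not the sequence of steps within a visit.
- **That young children are the main group at risk.** The sentence stands in the paragraph on subjects aged 18 and older. It is not expressly confined to them, and 10.5 also has parents dose in the office, but the text singles out no age group.

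**Conclusion.** The order in 10.7 is wrong as written and is probably an inversion. The consequence is minor: at most one unneeded application per wart already clear at Day 29 (9 doses rather than 8), and none where the investigator acts on clearance seen before the dose.

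That bound assumes the listed dosing days are kept and the wart was not stopped earlier. The documents do not give the number of warts clear at Day 29, so no study total can be stated.

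The Day 29 reading follows an application, with an effect of unknown size and direction. The SAP 3.4 mismatch is one of wording, and it would be wrong to conclude that an efficacy endpoint loses its baseline. The SAP 3.11.1 count omits one given treatment for each such wart. A percentage error in compliance cannot be derived, because the denominator is undefined.

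Confidence is high on what the text says. The consequences are possible rather than certain.

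**What to change.** Reword 10.7 so that, on Day 1 and Day 29 of each course, the PWA and wart dimensions are completed before any in-office application, as the skin reaction assessments already are. State that a wart scored PWA=0 is not dosed at that visit. The SAP 3.4 baseline and the same-day rule in SAP 3.11.1 then work as written, and neither needs editing for this point.

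The cost is a one-sentence amendment, submission to the Central IRB under Protocol 16.1 and a memo to sites. Existing steps are reordered; no visit or procedure is added. Home doses between visits are unaffected.

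Optionally, where source records already show the order used, flag in the listings the Day 29 PWAs that were read after dosing.

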10.8. Subject Instructions

An investigational center staff member will dispense a Subject Instruction Sheet to each subject at Visit 1 (Refer to [Appendix 1](#)).

Throughout the study, the subjects should:

- Continue their routine cleansing regimen except they should avoid vigorous scrubbing of the identified common warts (e.g., loofah, back brushes, scrubbing straps, abrasive washcloths, sponges and cleansing pads, etc.)
- Continue their routine cosmetics and skin care products
- Avoid exposing the identified common warts to excessive natural or artificial ultraviolet radiation (e.g., sunlight, tanning beds) and use sunscreen on the common warts, if excessive exposure cannot be avoided
- Avoid activities that might irritate the common warts.
- Avoid the use of self-tanning lotions and spray tans near the common warts.
- Bring the subject instruction sheet and subject diary with them to each visit.
- Follow all instructions for the proper application of the A-101 study medication when applying product at home and document all at home treatment applications on the subject diary.

On study visit days, the subjects should:

- Wear loose fitting clothing to the visit (Note: clothing that comes in contact with the study medication may be bleached)
- Not apply any topical products to the identified common wart within **12 hours** prior to the visit (Note: routine cleansing products are allowed)
- After the completion of any study visit where a study medication treatment was performed
DO NOT:
 - Wash/submerge the treated common wart for at least **6 hours**
 - Apply any topical products to the treated common wart for at least **6 hours**.
 - Parents/legal guardians of children must ensure that the child does not put the treated area in their mouth, or eyes, until completely dry after the application. If the treated area is not completely dry 10 minutes after the application, the area should be blotted dry.

10.9. Other Study Supplies

Aclaris Therapeutics, Inc. will provide:

- An appropriate ruler, or other instrument, for measuring of all common wart dimensions;
- Nitrile gloves
- Zip top plastic bags
- Supplies and instructions for collecting, labeling, shipping and result reporting for the clinical laboratory tests from ACM Laboratories;

Aclaris Therapeutics, Inc.

Protocol Number: A-101-WART-303

Protocol Version 3: 14 February 2019

10.10. Dose Modification

If a subject refuses to have a study medication treatment, the investigator must report the visit number, visit date, and state the reason the subject refused to allow treatment in the subject's CRF.

If the subject's refusal is associated with an AE, the investigator must also report the event on the appropriate CRF.

10.11. Breaking the Blind

Not applicable as this is an open label study.

11. PREVIOUS AND CONCOMITANT THERAPIES

11.1. Previous Therapy

During Visit 1, the investigator or designee will question the subject to ensure they have not used any excluded therapies within the specified period prior to Visit 2 to the identified common warts:

- Intralesional Therapy
 - Immunotherapy (*e.g.*, *Candida* antigen, mumps antigen, *Trichophyton* antigen); 8 weeks
 - Anti-metabolite therapy (*e.g.*, bleomycin, 5-fluorouracil); 8 weeks
- Systemic Therapy
 - Immunomodulatory/immunosuppressant therapy (*e.g.*, etanercept, alefacept, infliximab); 16 weeks
 - Glucocortico-steroids (inhaled and intra-nasal steroids are permitted); 28 days
- Topical Therapy
 - LASER (*e.g.*, pulsed-dye laser [PDL], light (*e.g.*, intense pulsed light [IPL], photodynamic therapy [PDT], other energy-based therapy); 6 months
 - Immuno-therapy (*e.g.*, imiquimod, squaric acid dibutyl ester [SADBE], etc.); 12 weeks
 - Antimetabolite therapy (*e.g.*, 5-fluorouracil); 8 weeks
 - Retinoids; 90 days
 - Liquid nitrogen, electrodesiccation, curettage; 60 days
 - Over-the-counter (OTC) wart therapies and cantharidin; 28 days

